12.6.2. Laboratory Results

Descriptive statistics (N, mean, standard deviation [SD], median, first and third quartiles [Q1, Q3], minimum, and maximum) will be provided for each continuous laboratory test by treatment arm. Values will be summarized at baseline, at each on-treatment time point, for the minimum and maximum on-treatment values, for the last on-treatment value, and for the last on-study value. These results will also be presented as boxplots.

Dichotomous laboratory endpoints will be descriptively analyzed using counts and percentages.

12.7. Pharmacokinetic and Exposure-Response Analyses

Plasma BCV concentrations will be listed and summarized using descriptive statistics (including N, mean, SD, percent coefficient of variation [%CV], median, minimum, and maximum). Concentrations that are BLQ will be treated as zero (0) for the purposes of descriptive statistics.

The plasma BCV concentration-time data will be included in a population PK analysis to characterize plasma BCV PK, evaluate the impact of covariates of interest, and derive individual post hoc PK exposure parameters (plasma BCV AUC and C_{max}). An existing population PK model developed with data from six previous BCV studies (CMX001-115, CMX001-201,

CMX001-301, CMX001-202, CMX001-304, and CMX001-350) will be applied. If necessary, additional modelling may be completed with data from only this study or by combining data from this study with data from previous studies. Population PK analyses will be completed in NONMEM[®]. A Population PK analysis plan will be written separately from the study SAP.

The post hoc plasma BCV AUC and C_{max} estimates from the population PK model will be used to characterize the potential impact of plasma BCV exposure on clinical safety, virologic, and mortality endpoints, and to evaluate the modifying influence of various covariates of interest on these relationships and endpoints. Data from this study may be analyzed alone or in combination with data from previous studies for exposure-response analyses. Exposure-response analysis may include time-to-event, logistic regression, linear regression, and/or nonlinear regression models, and analyses will be completed in R, S-plus, and/or SAS. An exposure-response analysis plan will be written separately from the study SAP.

12.8. Other Analyses

12.8.1. Subject Enrollment and Analysis Sets

The number and percent of subjects randomized in each country and by each investigator will be summarized overall and by treatment arm. The denominator for this calculation will be the number of ITT subjects.

A summary of analysis sets will present the number of subjects screened, randomized, and included in each analysis set (with summary of reasons for exclusion from each analysis set) by treatment arm.

12.8.2. Demographics and Baseline Characteristics

Subject demographic data (e.g., age, sex, race, and ethnicity) and baseline characteristics (e.g., body weight, height, body mass index, AdV viral load, disease for which HCT was conducted, pre-transplant conditioning regimen, source of graft, type of graft) will be summarized by treatment arm and overall using descriptive statistics (N, mean, SD, median, Q1, Q3, minimum, and maximum) for continuous data and using the number and percent of subjects for categorical data. Age is calculated in years at the date of randomization. Summaries of demographic data and baseline characteristics will be provided for the ITT, mITT, PP, and safety analysis sets.

12.8.3. Prior and Concomitant Medications

Medications started prior to Day 1 and those taken on or after Day 1 will be summarized separately (number and percentage of subjects) by treatment arm, Anatomical Therapeutic Chemical classification second-level category, and World Health Organization generic name, using the safety analysis set.

12.8.4. Study Drug Exposure/Compliance

Duration of exposure to BCV will be defined as: last dose date – first dose date + 1, regardless of temporary interruptions in study drug administration, and will be expressed in days. Duration of exposure to BCV will be summarized using descriptive statistics (N, mean, SD, median, Q1, Q3, minimum, and maximum) and as the number and percent of subjects exposed for BIW durations

(decreasing cumulative) for the safety analysis set. Other measures of exposure/compliance may be presented as defined in the SAP.

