
Objectives:
 
This study is designed to assess the safety, overall tolerability, and antiviral activity of “short course” BCV therapy, as compared with current standard of care (SoC), for the treatment of adenovirus (AdV) infections in high-risk (i.e., T cell-depleted) pediatric allogeneic hematopoietic cell transplant (HCT) recipients. A virologic response-driven approach to the duration of treatment will be evaluated, in which subjects randomized to BCV therapy are treated until AdV viremia is confirmed as undetectable or until a maximum of 16 weeks of therapy, whichever occurs first.
 
Primary Objective:
 
The primary objective of the study is to compare the safety, overall tolerability, and virologic response of BCV vs. SoC for the treatment of AdV infection in high-risk pediatric allogeneic HCT recipients.
 
Secondary Objectives:
 
 • To assess the incidence of and time to all-cause, non-relapse, and AdV-associated mortality in pediatric subjects treated with BCV vs. SoC • To assess the correlation between virologic response and clinical outcome • To describe the incidence of and time to virologic relapse in subjects who have previously achieved undetectable AdV viremia • To assess resolution or progression in clinical symptoms associated with AdV disease (i.e., resolution of all disease to no disease among subjects with probable or definitive AdV disease at baseline and progression from no disease to any probable or definitive AdV disease among asymptomatic subjects at baseline) • To assess the correlation between AdV hexon “serotype,” virologic response, and clinical outcome • To evaluate the emergence of viral resistance among subjects treated with BCV vs. SoC • To characterize plasma BCV pharmacokinetic (PK) profiles and evaluate the impact of covariates of interest on PK • To characterize the potential impact of plasma BCV exposure on clinical safety, virologic, and mortality endpoints, and to evaluate the modifying influence of various covariates of interest on these relationships and endpoints

- To assess virologic response in other non-plasma biologic compartments (urine, stool, respiratory secretions), as well as the association between detectable AdV viral load in these compartments at AdV viremia clearance with subsequent AdV viremia relapse

Exploratory Objectives

- To assess the correlation between baseline HCT co-morbidity index and clinical outcome

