Pediatric subjects have responded to BCV therapy. Study CMX001-304 enrolled 201 subjects (130 pediatric, 71 adult) with disseminated AdV disease or with asymptomatic viremia or localized AdV infection who were at risk for progression to disseminated AdV disease. Subjects were treated with BCV for 12 weeks. In this study, pediatric subjects had improved clinical outcomes compared with adult subjects (all-cause mortality at Week 36 was 39% in pediatric subjects vs. 63% in adults). Key differences between these two groups at baseline suggest that the adults who enrolled in this trial had poorer prognoses than the children (e.g., indication for transplantation, frequency of T cell depletion). Additionally, the time from transplant to BCV initiation was longer for adults (median 94 days) than pediatric subjects (median 53 days), which may reflect earlier diagnosis in the setting of screening protocols that are common at pediatric transplant centers. Pediatric subjects tolerated BCV better than adults and had longer median duration of BCV therapy (78 days vs. 38 days in adults).

Because pediatric recipients of T cell-depleted allogeneic HCT are at very high risk for AdV infection and progression to serious disease, they are among the most in need of new treatment options, and have demonstrated reasonable tolerability and responses with BCV-based therapy. Accordingly, this study will focus enrollment on this population most likely to benefit from treatment with BCV.

Subjects to be excluded are those with baseline comorbidities AdV who are unlikely to survive to Week 4, such as subjects with renal failure or a need for renal replacement therapy, those with pre-existing coagulopathy, sepsis requiring vasopressors, or the need for ventilator support.

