4.3.3.1. Rationale for BCV Dosage Regimen

BCV 2 mg/kg (up to 100 mg) BIW has been selected as the dosage regimen for this study. In the Phase 2 AdV pre-emption study (CMX001-202), there were trends for improved antiviral effect and survival (through 4 weeks post-end of treatment) with BCV 2 mg/kg (up to 100 mg) BIW compared with BCV 4 mg/kg (up to 200 mg) QW and placebo ([Grimley 2017](#)). In the subsequent open-label, single arm AdV treatment study (CMX001-304), BCV 2 mg/kg (up to 100 mg) BIW was associated with rapid virologic response; in the subset of pediatric HCT recipients remaining on-study at Week 4 and Week 6 (69 and 66 of 100 enrolled, respectively), 59% achieved undetectable plasma AdV viral load by Week 4 and 68% achieved undetectable plasma AdV viral load by Week 6 (Section 4.3.7). Rapid virologic response was associated with improved survival in subjects with disseminated AdV disease, and there were trends for an association between rapid virologic response and improved survival in subjects with asymptomatic or localized AdV disease (Section 4.3.7.1 and Section 4.3.7.2). Similar rapid virologic responses were observed with BCV 2 mg/kg BIW in the compassionate use setting ([Hiwarkar 2017](#)).

Efficacy and safety exposure-response analyses suggest that high plasma BCV exposures are not required for antiviral activity for AdV (Figure 1) and that lower oral doses may be associated with lower BCV-associated AEs (see the BCV Investigator's Brochure for details). Actions taken to minimize PK variability and avoid high plasma BCV exposures in this study include BCV dose reduction for subjects receiving concurrent cyclosporine to account for drug interaction (Section 8.6). Overall exposure will be decreased by applying treatment only until AdV DNA is cleared from the plasma, as explained below.

Figure 1: Relationship between Weekly Plasma BCV AUC and Achievement of Undetectable Plasma AdV Viral Load

Abbreviations: BCV AUC = brincidofovir weekly area under plasma concentration-time curve; UND4 = undetectable plasma AdV viral load at Week 4 (0 = no, 1 = yes).

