8.3.1. BCV Dosing Algorithm Based on Virologic Response

The duration of BCV treatment will be determined using results from the designated central virology laboratory only.

In the absence of toxicity requiring dose interruption, BCV will be administered BIW for up to 16 weeks or until plasma AdV viremia is confirmed as undetectable (i.e., two consecutive plasma viral load results of “undetectable” as reported by the designated central virology laboratory). The confirmatory sample must be drawn no sooner than 7 days (6 full calendar days) and no later than 14 days (13 full calendar days) after the last sample was drawn. Once AdV viremia is confirmed as undetectable, BCV will be discontinued. If AdV viremia is subsequently confirmed at ≥ 1000 copies/mL by the designated central virology laboratory, BCV dosing may be re-initiated, unless precluded by the BCV toxicity guidelines (see Section 8.4). See [Appendix 3](#) for a flow chart of the BCV dosing algorithm.

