8.4. Re-initiation of BCV Dosing for AdV Viremia

Subjects who stop BCV therapy due to confirmed undetectable AdV viremia may re-initiate treatment with BCV if AdV viremia is subsequently confirmed at ≥ 1000 copies/mL by the designated central virology laboratory. For the purposes of re-initiating BCV therapy, “confirmed viremia ≥ 1000 copies/mL” is defined as two consecutive results ≥ 1000 copies/mL from the designated central laboratory, with the second sample drawn at least 48 hours after the first sample. BCV dosing will be resumed at the same dose and dose frequency the subject was receiving when BCV therapy was stopped (e.g., if BCV dosing had been consolidated to QW administration for toxicity management purposes, the subject would resume at the QW dose). Subjects should be managed as per the toxicity monitoring and management criteria as outlined in Section 8.3.2.

Subjects who permanently discontinue BCV for toxicity reasons are not eligible to re-initiate BCV dosing.

8.5. Access to BCV after Week 16

Subjects randomized to the BCV arm may receive up to 16 weeks of therapy with BCV (through Week 16 post-randomization). Treatment with BCV may not be extended past Week 16 under this protocol. Therefore, investigators wishing to extend or re-initiate treatment with BCV for a subject after Week 16 will need to request access to the drug through the local NPP (or other expanded access program), where available. If applicable, approval for access to BCV through the NPP should be secured prior to the subject completing the Week 16 assessment to ensure continuity of care.

Subjects randomized to the SoC arm are not allowed to receive BCV during the 16-week treatment period, whether under this protocol or through an expanded access mechanism. After completion of the Week 16 assessment, investigators may request access to BCV through the local NPP (or other expanded access program), where available.

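### Section 12.8.4 measures BCV exposure from first to last dose and ignores gaps, so it overstates time on drug for subjects who stop at clearance and later restart

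*Combined protocol and SAP*

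**What the plan says.** Section 12.8.4 fixes one exposure measure, "last dose date – first dose date + 1, regardless of temporary interruptions in study drug administration", in days. It is summarised for the safety set with descriptive statistics and with a decreasing cumulative table of the "number and percent of subjects exposed for BIW durations". On anything further the section says only: "Other measures of exposure/compliance may be presented as defined in the SAP".

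The treatment rules allow more than one course. Section 8.3.1: "Once AdV viremia is confirmed as undetectable, BCV will be discontinued". Section 8.4: "Subjects who stop BCV therapy due to confirmed undetectable AdV viremia may re-initiate", subject to confirmed recurrence at 1000 copies/mL or more. Section 8.5 ends protocol treatment at Week 16. Section 12.8.4 mentions temporary interruptions but does not say how a clearance stop followed by a restart is handled.

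Duration is part of the study question. The Synopsis states: "A virologic response-driven approach to the duration of treatment will be evaluated". Section 4.3.3.1 gives the reasoning: "Overall exposure will be decreased by applying treatment only until AdV DNA is cleared from the plasma".

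**The concern.** First-to-last-dose duration suits a single continuous course. Here a stop and a possible restart are built into the design, and the only committed measure cannot tell a long continuous course from two short courses with weeks off drug between them. A re-treated subject then appears in the exposure table as a long-course subject. The same formula also absorbs toxicity interruptions of at least 7 days (Section 8.3.2).

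The plan expects exposure to fall because treatment ends at clearance. To see how far it fell, a reader needs time actually on drug, and no measure of that is promised.

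**Working it through.** The documents state no expected exposure duration, so there is no figure to reproduce. The check applies the 12.8.4 formula to dose calendars and compares it with the sum of the course durations (last minus first plus 1 within each course).

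**Inputs from the documents:** twice-weekly dosing at alternating 3- and 4-day intervals (8.2); stop at confirmed clearance (8.3.1); restart allowed (8.4); nothing beyond Week 16 (8.5); a cited cohort with median time to clearance of 4 weeks, range 2 to 9 (4.4).

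**Assumed:** course lengths, gap lengths and the share of subjects who restart.

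**One subject, 4 weeks on, 4 off, 3 on.**
- Course 1 doses: days 1, 4, 8, 11, 15, 18, 22, 25. Duration 25 − 1 + 1 = 25.
- Course 2 doses: days 57, 60, 64, 67, 71, 74. Duration 74 − 57 + 1 = 18.
- Formula in 12.8.4: 74 − 1 + 1 = 74 days. Sum of courses: 25 + 18 = 43 days. Excess 31 days; ratio 74/43 = 1.72.

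On this calendar a gap of *g* weeks adds 7*g* + 3 days, because the last dose of the first course falls 3 days before the end of its final week.

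| On / off / on (weeks) | 12.8.4 formula | Sum of courses | Excess | Ratio |
|---|---|---|---|---|
| 4 / 2 / 4 | 67 | 50 | 17 | 1.34 |
| 4 / 4 / 3 | 74 | 43 | 31 | 1.72 |
| 4 / 8 / 3 | 102 | 43 | 59 | 2.37 |

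**Arm level.** Simulation of 94 BCV subjects: first course 2 to 7 weeks, gap 2 to 6 weeks, second course 2 to 4 weeks, all in whole weeks, equally likely and capped at Week 16. Cells show the 12.8.4 formula against the sum of courses.

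| Share restarting | Mean days | Median days | Share at 56 days or more |
|---|---|---|---|
| 0% | 28.4 vs 28.4 | 28.2 vs 28.2 | 0% vs 0% |
| 10% | 33.3 vs 30.2 | 30.8 vs 30.3 | 9% vs 3% |
| 20% | 38.4 vs 32.2 | 33.9 vs 32.2 | 18% vs 7% |
| 30% | 43.2 vs 33.9 | 37.6 vs 33.8 | 27% vs 10% |
| 50% | 53.1 vs 37.6 | 49.6 vs 37.6 | 45% vs 17% |

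The means can be checked by hand. The average gap is 4 weeks, so each restart adds 7 × 4 + 3 = 31 days on average, and the mean rises by 31 times the share restarting: 3.1, 6.2, 9.3 and 15.5 days.

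The distortion sits in the mean and in the upper tail of the cumulative table. The median moves little until restarting is common.

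**The case against.** The strongest reply concerns scope. The formula is exact for one uninterrupted course; only subjects who clear, relapse and restart before Week 16 carry the between-course gap, and the documents do not give their number. The rule is openly stated. The output is descriptive. Section 5.3.2 already lists time to first confirmed undetectable viremia, which tracks first-course length unless toxicity ends treatment sooner, and virologic relapse, which shows who may become eligible to restart. Section 12.8.4 also leaves room for other measures, and the text reviewed contains no separate SAP section on exposure, so an omission there cannot be shown. All of this stands and limits the point. It does not remove it: the permission commits to nothing, and neither listed endpoint measures time on drug after a restart.

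A reader might infer that the trial as a whole will misreport its short course. The documents do not support that, because single-course subjects are reported correctly and the number of restarts is unknown. A reader might also infer that readings of toxicity against duration will be wrong. No such analysis is planned: exposure-response work uses modelled plasma AUC and Cmax (12.7), and adverse events are summarised by time window (12.6.1). Nor do the documents plan a comparison with the 78-day paediatric median in Section 4.3.2, or say how that median was computed; if it was first to last dose, the current formula is the like-for-like one.

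One practical objection shapes the fix. Removing toxicity interruptions from time on drug would need a rule that separates a minimum 7-day hold from an ordinary once-weekly dosing interval, since the two have the same length.

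**Conclusion.** The point holds for subjects who restart. For them the stated rule counts drug-free weeks as BCV exposure, with an overstatement of 1.3- to 2.4-fold in the worked examples. For the arm, the mean and the long-duration rows of the cumulative table are inflated by an amount that depends on the restart rate and the gap length. Both are assumptions here, so the arm-level figures show a range and are not a forecast. Single-course subjects are unaffected by the gap, and no efficacy or inferential result changes. It is worth correcting before database lock because treatment duration is something the trial says it will evaluate, but it is a reporting matter and does not threaten the trial's conclusions.

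**What to change.** In Section 12.8.4, keep the present formula and label it span of treatment. Commit to four further measures:

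- (a) first-course duration: first dose to the last dose before the clearance stop, permanent discontinuation or Week 16;
- (b) total time on BCV: the sum of course durations, excluding intervals between a clearance stop and re-initiation;
- (c) number of re-initiated courses;
- (d) number of doses and cumulative mg/kg.

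Base the decreasing cumulative table on (b).

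Measure (d) reflects toxicity interruptions without a rule to separate a 7-day hold from a weekly interval. It needs both parts: the consolidated once-weekly regimen in Table 6 gives the same weekly amount in half as many doses (for example 2 × 2 = 4 mg/kg), so a dose count alone would mislead.

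The cost is a change to Section 12.8.4 with matching SAP text, and a few extra derivations and tables. Section 8.2.1 already has the date and time of every dose recorded in the eCRF, so no new data are needed. Section 12 allows SAP amendments until the lock for the primary analysis.

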12.8.5. Subject Disposition

A summary of subject disposition will be provided by treatment arm using the ITT analysis set. This summary will present the number and percent of subjects who:

- complete the study through Week 16
- do not complete the study through Week 16 (with summary of reasons)

12.9. Subgroup Analyses

The primary and all-cause mortality endpoints will be analyzed by various subgroups, including, but not limited to, each of the stratification factors, sex, age, race, transplant characteristics, underlying disease (malignant, non-malignant), advanced disease status, and investigator's intended SoC selected at the time of randomization. Multivariate modelling will be considered and defined in the SAP.

13. QUALITY CONTROL AND QUALITY ASSURANCE

13.1. Quality Controls and Study Monitoring

Quality controls are incorporated into project management activities conducted by Chimerix (or its designee), including the monitoring and verification of clinical and safety data.

Each investigational site will be subject to an assessment of the adequacy of site facilities, including responsibilities as related to the study and protocol requirements.

The progress of the study will be monitored by periodic onsite visits and frequent communications between Chimerix (or designee) and the investigator. A monitor assigned to the investigational site is responsible for assessment of the progress of the study, review and verification of study data collected, and identifying and assisting in resolution of issues. The objectives of monitoring procedures are to verify that study data are accurate, authentic and complete; that the safety and rights of subjects are being protected; and, that the study is conducted in accordance with the approved protocol (including any amendments), International Conference on Harmonisation (ICH) GCP and applicable regulatory requirements.

The investigator and study staff will allocate time to the monitor as required during on-site monitoring visits. The monitor will continue to support the investigational site between monitoring visits.

13.2. Quality Assurance Audits and Regulatory Inspections

Authorized representatives of Chimerix (or its designee), a regulatory authority, or the applicable EC may visit the site to perform audits or inspections, including source data verification. The purpose of such an audit or inspection is to systematically and independently examine all study-related activities and documents to determine whether these activities were conducted, and data were recorded, analyzed, and accurately reported according to the protocol, GCP, and applicable regulatory requirements. If such an audit or inspection occurs, the investigator will allow the auditor(s) or inspector(s) direct access to all source documents, eCRFs, and other study documentation for source data check and/or on-site audit/inspection, and will allocate his or her time and the time of his or her staff to the auditor or inspector, as required. The investigator should notify Chimerix immediately if contacted by a regulatory agency intending to conduct an inspection.

